**Patient withdrawal from the study / Stopping rules:**

Study treatment must be discontinued for any patient if the investigator determines that continuing would result in a significant risk for that patient. The following conditions/events may be considered sufficient to support a decision about the study drug discontinuation in individual cases:

- Adverse event/serious adverse event
- Abnormal laboratory value(s) or abnormal test result(s)
- Withdrawal of informed consent
- Pregnancy
- Use of prohibited other investigational medications
- Deviations from the prescribed dose regimen for the study drug
- Any other protocol deviation that results in a significant risk to the patient's safety

Discontinuation of the study drug must be recorded along with the patient information in REDCap, giving the date and primary and secondary reasons for stopping study treatment. The investigator must also contact the Institutional Review Board at the study site (University of California at San Francisco Multiple Sclerosis Center) to register the patient's discontinuation of randomized study drug.

Patients may voluntarily withdraw from the study for any reason at any time. They may be considered withdrawn if they state an intention to withdraw, fail to return for visits, or become lost to follow-up for any other reason.

For patients who are lost to follow-up (i.e. those patients whose status is unclear because they fail to appear for study visits without stating an intention to withdraw), the investigator should show "due diligence" by documenting in the source documents steps taken to contact the patient, e.g. dates of telephone calls, registered letters, etc.

If premature withdrawal occurs for any reason, the investigator must make every effort to determine the primary reason for a patient's premature withdrawal from the study and record this information with the patient's research data in REDCap as well as report this withdrawal to the Institutional Review Board and FDA CDER, if deemed necessary by the committee.

Patients will be considered to have completed the study if they attend all protocol specified visits and complete all assessments. A patient who discontinues the study medication for any reason, including an adverse event must complete a Safety Follow-Up visit. Any patient still in screening at the time 50 patients have been enrolled will be allowed to continue screening to determine if they will be eligible to enter the study, provided all screening assessments are complete and the randomization visit can occur on or before the designated end of subject recruitment date. The investigator must provide follow-up medical care for all patients who are prematurely withdrawn from the study or must refer them for appropriate ongoing care.

The study can be terminated at any time for any reason by the investigator. Should this be necessary, each patient should be seen as soon as possible and treated as described for a prematurely withdrawn patient. The investigator may be informed of additional procedures to be followed in order to ensure that adequate consideration is given to the protection of the patient's interests. The investigator will be responsible for informing the Committee on Human Research of

the trial's early termination.

## 15 STATISTICAL METHODS AND CONSIDERATIONS

Prior to the analysis of the final study data, a detailed Statistical Analysis Plan (SAP) will be written describing all analyses that will be performed. The SAP will contain any modifications to the analysis plan described below.

### 15.1 Data Sets Analyzed

All eligible patients who are randomized into the study and receive at least one dose of the study drug (the Safety Population) will be included in the safety analysis.

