### 4 STUDY DESIGN

#### 4.1 Study Overview

This is a 6-month randomized, single center, double blinded, delayed start study in 50 patients with relapsing remitting multiple sclerosis and identified injury to the anterior visual pathway.

Patients will be randomized 1:1 into two groups: Group A and Group B. Group A will receive 180 days of Bazedoxifene while Group B will receive 90 days of placebo followed by 90 days of Bazedoxifene. Patients will receive two fixed oral tablets of 20mg Bazedoxifene (Conbriza) daily (to be taken at the same time). Patients will be permitted to remain on their standard disease modifying treatment during the course of the study.

Screening data will be reviewed to determine subject eligibility. Subjects who meet all inclusion criteria and none of the exclusion criteria will be entered into the study

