## 6 SUBJECT SELECTION

### 6.1 Study Population

Subjects with a clinically definite diagnosis of MS—according to the 2017 revised McDonald Criteria (Thompson et al., 2017)—who meet the inclusion and exclusion criteria will be eligible for participation in this study.

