## 13 PROTOCOL VIOLATIONS

A protocol violation occurs when the subject, investigator, or investigator fails to adhere to significant protocol requirements affecting the inclusion, exclusion, subject safety and primary endpoint criteria. Protocol violations for this study include, but are not limited to, the following:

Failure to meet inclusion/exclusion criteria

Use of a prohibited concomitant medication

Failure to comply with Good Clinical Practice (GCP) guidelines will also result in a protocol violation. The PI will determine if a protocol violation will result in withdrawal of a subject.

When a protocol violation occurs, it will be discussed with the investigator and a Protocol Violation Form detailing the violation will be generated. This form will be signed by a Sponsor representative and the Investigator. A copy of the form will be filed in the site's regulatory binder and in the Sponsor's files.

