### 15.3 Analysis of Primary Endpoint

Data will be analyzed per protocol utilizing an intention to treat approach including all patients randomized to the study for the principal analysis. Loss to follow up will be accounted for using standard statistical methods. The principal analysis will be performed using mixed effects linear regression model controlling for clustering by eye.

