### 15.4 Analysis of Secondary Endpoints

Secondary endpoints will be analyzed using the same methods as primary endpoints.

Safety and tolerability data will be summarized by treatment group.

Adverse event rates will be coded by body system and MedDra classification term. Adverse events will be tabulated by treatment group and will include the number of patients for whom the event occurred, the rate of occurrence, and the severity and relationship to study drug.

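### The Safety Population is restricted to eligible patients, so read literally a patient dosed in breach of the entry criteria is left out of the safety analysis

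*Combined protocol and SAP*

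**What the plan says.** Section 15.1 contains one analysis-set definition, the Safety Population: "All eligible patients who are randomized into the study and receive at least one dose of the study drug (the Safety Population". These patients "will be included in the safety analysis".

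Two earlier sections give eligibility its meaning. Section 4.1 states: "Subjects who meet all inclusion criteria and none of the exclusion criteria will be entered into the study". Section 6.1 says that subjects with the diagnosis "who meet the inclusion and exclusion criteria will be eligible for participation in this study".

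Section 13 names as a protocol violation "Failure to meet inclusion/exclusion criteria". On the consequence it says: "The PI will determine if a protocol violation will result in withdrawal of a subject".

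For efficacy, Section 15.3 describes an intention-to-treat approach "including all patients randomized to the study for the principal analysis". For safety, Section 15.4 says: "Safety and tolerability data will be summarized by treatment group". It adds no rule for patients who were dosed but not eligible.

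**The concern.** A safety set normally takes in everyone exposed, because harm from a drug does not depend on whether the patient should have been given it. Here the set carries an extra filter, and the protocol itself foresees patients who would fail that filter after being randomized and possibly dosed.

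The patients affected are not a neutral subset. Exclusions 22 to 30 in Section 6.3 cover, among others, past venous or arterial thromboembolism, known thrombophilic disorders, undiagnosed uterine bleeding, estrogen-dependent neoplasia and hepatic disease. A patient who passes screening despite one of these and then has a related event is among the most informative safety cases in the trial. Tolerability and safety are the second and third key secondary objectives (Section 3.2), so the tables built on this set carry weight.

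**Working it through.** **Textual check.** The plan states no figure on this point, so there is none to reproduce. The question is whether a patient can satisfy every step below, and each step rests on the documents.

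1. *Conditions for the safety set (15.1):* eligible, and randomized, and at least one dose.
2. *Meaning of eligible (4.1, 6.1):* all inclusion criteria met and no exclusion criterion present.
3. *Can a patient be entered without being eligible?* Section 13 lists this as a violation, so the protocol allows for it.
4. *Must that patient leave before dosing?* No. Section 13 leaves withdrawal to the PI. Section 10.2 randomizes and dispenses at the same visit, so a breach found later is found after supply of the drug.
5. *Does another section return the patient to the safety analysis?* No. Section 15.4 only says that the summaries are by treatment group.
6. *How does efficacy treat the same patient?* Section 15.3 takes all randomized patients, with no eligibility condition.

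On the literal wording, then, a dosed ineligible patient fails step 1 for safety and passes step 6 for efficacy. A dosed-only safety set is ordinarily no larger than an intention-to-treat set, so a smaller safety set is not in itself a fault. The fault is that eligibility is required for safety alone.

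**Illustration of size.** Inputs: 25 patients per group (15.6) and 1:1 allocation (4.1). Assumptions, not in the documents: all 25 are dosed, one is ineligible, and that patient has the only event of its kind. Limits are exact binomial (Clopper-Pearson), 95% two-sided. For 0 events in n the upper limit is 1 − 0.025^(1/n).

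| Set | All dosed | Ineligible patient removed |
|---|---|---|
| One arm | 1/25 = 4.0% (0.1% to 20.4%) | 0/24 = 0%, upper limit 1 − 0.025^(1/24) = 14.2% |
| Both arms | 1/50 = 2.0% (0.1% to 10.6%) | 0/49 = 0%, upper limit 1 − 0.025^(1/49) = 7.3% |

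The pooled row is relevant because Section 4.1 plans for both groups to receive bazedoxifene at some stage.

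*Range.* With 1 to 5 ineligible dosed patients in an arm, the denominator falls from 25 to between 24 and 20. The loss of denominator is minor. What matters is that an observed event can become none observed, with the upper limit falling from 20.4% to 14.2% in one arm.

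**The case against.** The best defense is that *eligible* describes status at entry. Section 8.1 speaks of eligible patients being randomly assigned, Section 4.1 expects only those who meet the criteria to enter, and Section 14 treats screening as the point at which eligibility is settled. On that usage the phrase covers everyone cleared at screening and randomized. Nothing in the plan provides for judging eligibility again after dosing or for striking a patient from the safety tables. This reading is plausible, and the word may be loose drafting. It does not remove the literal condition, though, and Section 13 shows that the protocol expects exceptions.

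Other points on that side stand in whole or in part:

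- *Events are still captured.* Sections 9.1.7 and 11.1 record adverse events throughout, and Section 11.2.1 documents every SAE and sets out reporting to the FDA and the local committee, with no eligibility condition. A reader might infer that an event in an ineligible patient would go unrecorded or unreported; the documents do not support that.
- *The PI's decision does not set membership.* A reader might infer that withdrawal decisions under Section 13, together with the biweekly data review in Section 14, let the investigator shape the safety set. But a dosed patient who is withdrawn still meets the dosing condition. Membership turns on eligibility and dosing, not on withdrawal.
- *The contrast with efficacy needs care.* The sentence in Section 15.3 opens by mixing per-protocol and intention-to-treat language. Its explicit inclusion of all randomized patients is what the contrast rests on.
- *A later SAP may change this.* Section 15 says that a detailed plan will follow and may modify these methods. No text in hand alters the definition.

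**Conclusion.** The point holds as a defect in the definition of the analysis set. As written, Section 15.1 can leave a dosed patient out of the safety analysis while Section 15.3 counts the same patient for efficacy, and the exclusions at issue mean that such a patient could be at higher risk. The consequence is confined to the safety set and the tables drawn from it.

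The size is illustrative only: 1/25 becoming 0/24, or 1/50 becoming 0/49, assuming one ineligible dosed patient with the sole event. The documents give neither an expected number of ineligible patients nor an event rate, so 4.0% is not a predicted bias. Nor do they say when eligibility breaches tend to come to light. A reader might infer that removal would usually follow an adverse event and so be related to outcome. That is possible, but it is not documented, and the conclusion does not need it.

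The change should be made: it is specific, costs almost nothing and closes off a possible bias before any event is known.

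**What to change.** In Section 15.1 delete *eligible* and define the Safety Population as every patient who has taken one or more doses of study drug. Add that eligibility violations are given in a separate listing, so that a reader can see which safety events occurred in such patients. Carry the same definition into the SAP.

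The cost is one deleted word and one short sentence, with no added visit or procedure. No new follow-up rule is needed for this purpose: Section 12.1 already encourages patients who stop study drug to complete their remaining visits, and Section 15.3 already keeps all randomized patients for efficacy.

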### 15.2 Demographic and Baseline Characteristics

The following demographic variables at screening will be summarized by dose level: race, gender, age, height and weight.

### 15.3 Analysis of Primary Endpoint

Data will be analyzed per protocol utilizing an intention to treat approach including all patients randomized to the study for the principal analysis. Loss to follow up will be accounted for using standard statistical methods. The principal analysis will be performed using mixed effects linear regression model controlling for clustering by eye.

### 15.4 Analysis of Secondary Endpoints

Secondary endpoints will be analyzed using the same methods as primary endpoints.

Safety and tolerability data will be summarized by treatment group.

Adverse event rates will be coded by body system and MedDra classification term. Adverse events will be tabulated by treatment group and will include the number of patients for whom the event occurred, the rate of occurrence, and the severity and relationship to study drug.

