OF ADMINISTRATION	tablets for the duration of treatment period (180 days for 'Early-start' group and 90 days for 'Delayed-start' group). Tablets will be over-encapsulated in gelatin capsules for proper blinding.
CONTROL PRODUCT, DOSE AND ROUTE OF ADMINISTRATION	Microcrystalline cellulose placebo Product will be taken daily via oral administration of 2 tablets for duration of the treatment period (first 90 days of 'Delayed-start' group ONLY). Tablets will be over-encapsulated in gelatin capsules for proper blinding.
DURATION OF SUBJECT PARTICIPATION AND DURATION OF STUDY	Subjects will be on study for up to 200 days Screening: 2 weeks Treatment: 6 months The total duration of the study is expected to be 24 months, which includes 18 months for subject recruitment.
CONCOMITANT MEDICATIONS	Allowed: MS disease modifying and symptomatic therapies, antidepressants (no adjustments within 2 months of baseline visit) Prohibited: hormone therapies (estrogen, testosterone, progesterone), hot flash therapies; lamotrigine, oxcarbazepine
EFFICACY EVALUATIONS	This study includes the following efficacy assessments: 
 
Detailed neurological examination, including the determination of EDSS score, will take place at the baseline and 6-month visits.
 
Magnetic Resonance Imaging (MRI) scans will be performed at the baseline, 3-month, & 6-month visits.
 
High and Low Contrast Visual Acuity (2.5% ETDRS) will be assessed at every visit.
 
Optical Coherence Tomography (OCT) will be performed at screening, baseline, and 6-month visits.
 
Full-field Visual Evoked Potential will be performed at every visit.
 
Cone contrast testing will be performed at baseline and 6 month visits.
 
 Note: Prior to each visit, participants should be reminded to bring with them any corrective lenses that they use on a regular basis for reading, distance, or both. If the participant does not have or if they forget their corrective lenses, a pair of trial lenses will be provided during the visit.
PRIMARY ENDPOINT	Remyelination assessed by the reduction of P100 VEP latency
SECONDARY ENDPOINTS	[Imaging]: Whole brain MTR, white matter MTR, white matter fractional anisotropy (FA), and MWF. [Functional]: Low-contrast letter acuity (LCLA)
OTHER EVALUATIONS	

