#### 3.2 Secondary Objectives

- The first key secondary objective is to assess whether latency delay at 180 days decreases to a greater extent in Group A (exposed to BZA for 90 days during both Stage 1 and Stage 2) when compared to Group B (exposed to placebo during Stage 1 and BZA for only 90 days during Stage 2).
- The second key secondary objective is to demonstrate the tolerability of BZA in this population. This will include special focus with regards to fatigue as this is a major symptom for patients suffering from multiple sclerosis.
- The third key secondary objective is to document the safety of BZA in this population of patients.
- The fourth key secondary objective of this study is to help assess which secondary and tertiary outcomes are likely to be informative for future remyelinating trials in multiple sclerosis.

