#### **5.3.5 Fatigue Assessment**

To ensure patient safety in daily activities, we will conduct a fatigue assessment at each of the visits indicated in Appendix-1, in order to monitor the degree of self-reported fatigue experienced.

The Modified Fatigue Impact Scale (MFIS) is a 21-item fatigue scale that measures the physical, cognitive, and psychosocial aspects of fatigue.

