## 14 DATA SAFETY MONITORING

Safety Data Monitoring throughout the trial: Since this trial is a single-site trial and the overseeing Principle Investigator will be present throughout the trial, a Data and Safety Monitoring Board is not deemed necessary. The study investigator will be responsible for monitoring safety data and adverse events recorded in the patient file and will be responsible for reporting such events to the FDA and IRB.

Safety assessments will be throughout patient visits to ensure patient welfare and safety in daily activities.

Such assessments will include:

- Physical Examination
- Vital Signs
- Height and Weight measurements
- Pregnancy and Assessments of Fertility
- Ophthalmologic Examination

- Fatigue Assessment - Health Status Questionnaire & MFIS
- Pharmacokinetics/Blood tests to assess potential abnormal increase of liver enzymes and serum triglycerides
- Lab tests to assess level of BZA in patient plasma to ensure that they are not abnormal

The Investigator will meet with the study staff biweekly to review safety as well as efficacy data collected from patient visits and assess the safety of the visits and study outcomes.

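### Fatigue is the stated focus of a key secondary objective, but no baseline-adjusted, placebo-controlled analysis of the fatigue scale is planned

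*Combined protocol and SAP*

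**What the plan says.** - **Objective.** Section 3.2, repeated in the synopsis: "The second key secondary objective is to demonstrate the tolerability of BZA in this population". It continues: "This will include special focus with regards to fatigue as this is a major symptom for patients suffering from multiple sclerosis".
- **Instrument.** Section 5.3.5, under Safety Evaluations: "The Modified Fatigue Impact Scale (MFIS) is a 21-item fatigue scale that measures the physical, cognitive, and psychosocial aspects of fatigue". The purpose given there is monitoring: "To ensure patient safety in daily activities, we will conduct a fatigue assessment at each of the visits indicated in Appendix-1". Section 14 lists it again among the safety assessments, as "Fatigue Assessment - Health Status Questionnaire & MFIS".
- **Not a listed endpoint.** MFIS is absent from section 5.2 and from the secondary endpoints in the synopsis.
- **Timing.** Sections 10.2 to 10.4 and Appendix 1 schedule MFIS at baseline, Month 3 and Month 6. Section 10.2 lists it ahead of dispensing.
- **Analysis.** Section 15.4 first applies the primary methods to secondary endpoints. It then gives safety and tolerability data a rule of their own: "Safety and tolerability data will be summarized by treatment group". The only further detail there concerns adverse event tables. The primary model in 15.3 is a mixed effects linear regression that controls for clustering by eye.
- **Exposure.** Under 4.1, Group B takes placebo for the first 90 days and BZA for the next 90, while Group A takes BZA throughout.

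**The concern.** The objective promises a demonstration, and the analysis section offers a description. To support a claim that BZA does not worsen fatigue, a plan needs a between-group estimate, an interval around it, and a statement of what result would count. None is given for MFIS: no score, time point, contrast, model, interval or criterion.

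The trial already collects what is needed: a pre-treatment score and a Month 3 score taken while Group B is still on placebo. Without a prespecified contrast at that visit, an unremarkable pair of group summaries could be reported as tolerability shown, although a sizeable worsening had not been ruled out. A summary by treatment group that is not split by stage would also mix Group B's placebo and BZA periods, because 15.4 does not say how the two stages are to be handled.

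**Working it through.** **The plan's own figure.** There is none for fatigue or tolerability. The only power figure is 90% in 15.6, for VEP latency with 25 per group and two-sided alpha 0.05. No SD or absolute difference is given, so it cannot be reproduced. It can only be turned into the standardised difference it implies: (1.960 + 1.282) × √(2/25) = 0.917 SD. It says nothing about MFIS.

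**Which rule covers MFIS?** There are two candidates in 15.4.

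1. *MFIS as tolerability data.* This follows from its place in 5.3.5 and section 14. The stated rule is then a summary by group, with no comparison specified.
2. *MFIS under the secondary-endpoint rule.* The primary model then applies. It clusters by eye, but MFIS gives one score per patient, so there is no eye-level structure to model. It also names no baseline covariate.

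Neither reading yields a baseline-adjusted comparison at Month 3.

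**What such a comparison would deliver.** Inputs: 25 per group (15.6) and 1:1 allocation (4.1). Assumptions: no dropout, and a baseline-to-Month 3 correlation r. The documents give no MFIS SD or correlation, so results are in SD units over a range of r.

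- Unadjusted 95% half-width: t(0.975, 48) × √(2/25) = 2.011 × 0.2828 = 0.569 SD.
- Adjusted for baseline: 0.569 × √(1 − r²).
- Difference detectable at 80% power (normal approximation): (1.960 + 0.842) × 0.2828 × √(1 − r²).

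| Assumed r | √(1 − r²) | 95% half-width (SD) | Detectable at 80% power (SD) | Power for 0.5 SD |
|---|---|---|---|---|
| unadjusted | 1.000 | 0.569 | 0.79 | 42% |
| 0.5 | 0.866 | 0.493 | 0.69 | 53% |
| 0.6 | 0.800 | 0.455 | 0.63 | 60% |
| 0.7 | 0.714 | 0.406 | 0.57 | 70% |
| 0.8 | 0.600 | 0.341 | 0.48 | 84% |

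If the observed means were identical, the unadjusted interval would still admit a worsening of 0.57 SD. At r between 0.6 and 0.8 the adjusted interval would admit 0.46 to 0.34 SD, which is 20% to 40% narrower. A margin tighter than the half-width could therefore be met only if the point estimate favoured BZA. Dropout would widen every interval.

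**The case against.** **No sentence says MFIS will only be summarised.** A reader might infer that the plan excludes MFIS from comparison. The documents do not go that far. Section 15 never names the scale, so the summary rule reaches it through its placement. Describing data by group also does not forbid change from baseline or intervals. This stands, and it is why the point is put as a comparison not planned rather than one ruled out.

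**Fatigue is touched elsewhere.** Section 14 counts the Health Status Questionnaire as part of the fatigue assessment. That is the SF-36, a 5.2 endpoint, so 15.4 nominally applies the primary methods to it. Fatigue reported as an adverse event would be tabulated by group with rate, severity and relationship. It would therefore be wrong to say that fatigue receives no analysis. But 5.2.6 describes two SF-36 summary scores, physical and mental, and no fatigue score. The eye-clustered model fits SF-36 no better than MFIS, and adverse event tables are descriptive.

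**Placement under safety is not an error.** Section 5.3.5 gives a safety purpose, and tolerability data belong there. The difficulty is the analysis rule that comes with the placement.

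**A later SAP is promised.** Section 15 says a detailed one will precede the final analysis and may modify the plan. It could close the gap. No such text is in the document supplied, so this lowers the weight of the point without answering it.

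**The precision figures measure something narrower.** The 20% to 40% gain is that of adjusted over unadjusted estimation and rests on an assumed correlation. It does not measure the difference between a summary and a comparison. This is correct, and the figures are offered only as an illustration.

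**Conclusion.** The point holds in a limited form. A key secondary objective is to be demonstrated with a focus on fatigue, yet the only rule stated for tolerability data is a summary. The alternative rule brings a model that does not suit a per-patient score. On either reading, no baseline-adjusted, placebo-controlled fatigue comparison is specified, and there is no criterion for success.

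The illustrative size is a 95% half-width of about 0.57 SD unadjusted and about 0.46 to 0.34 SD adjusted. It assumes 25 per group, no dropout and a correlation of 0.6 to 0.8. Even the adjusted analysis has only 60% to 84% power for a 0.5 SD difference over that range, so it may not settle the question. It would show how much worsening remains possible.

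Two stronger inferences should be resisted. Month 6 is not a placebo contrast, because both groups are then on BZA under 4.1. The point also does not touch the primary efficacy analysis, the randomisation or the data collection. It is a worthwhile correction to one secondary analysis and to the claim attached to it.

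**What to change.** In 15.4:

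1. Name the fatigue analysis: MFIS total score at Month 3, Group A versus Group B as randomised, by patient-level ANCOVA with baseline MFIS total as covariate, reported as a difference with its 95% CI.
2. Report the Month 6 score in the same way, but label it as early versus delayed start and not as BZA versus placebo.

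In 3.2 and the synopsis, change *demonstrate* to *estimate* for tolerability. The alternative is to prespecify a margin for fatigue worsening and state that the 95% confidence limit on the side of worse fatigue must fall within it. If a margin is set, check it against the half-widths above before keeping the stronger verb.

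The cost is one extra analysis and a slightly more modest claim. No new visits, patients or measurements are needed. The change should be made before any unblinded data are seen, and it can go into the promised SAP if the protocol is not otherwise being amended.
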